### **Day 3** ( $\pm 1$ day)

- Collect a blood sample for assessment of biochemistry (site visit or local laboratory)
- Collect information on concomitant medications (site visit or telephone call)
- Collect information on any adverse events that have occurred since the previous visit (site visit or telephone call)
- Remind the patient to keep a record of all dosing, any concomitant medications that are taken, and any health problems that occur

**Days 7, 14, and 21** ( $\pm 1$  day for Day 7,  $\pm 2$  days for the remainder)

- Collect blood samples for assessment of the following (site visit or local laboratory):
  - Biochemistry
  - Hematology
- Collect information on any adverse events that have occurred since the previous contact (site visit or telephone call)
- Collect information on concomitant medications (site visit or telephone call)
- Remind the patient to do the following:
  - Keep a record of all dosing, any concomitant medications that are taken, and any health problems that occur
  - Day 21 only: Bring back the completed notes plus all medication containers, whether empty, partly used, or unopened

**Day 28 ( $\pm 2$  days) or Early Termination**

- Collect blood samples for assessment of the following:
  - Biochemistry
  - Hematology
  - Coagulation
  - Pregnancy testing (women of childbearing potential only)
- Collect a urine sample for urinalysis. Microscopic examination must be performed if dipstick test is outside the reference range for leukocyte, blood, nitrite or protein. (Note: for patients with sickle cell disease, samples are to be sent for microscopy if there is blood in the urine or three or more “plus signs” for protein.)
- Perform a symptom-oriented physical examination (to be completed by the principal investigator or a qualified delegate)
- Measure vital signs (heart rate, blood pressure, and body temperature).
- Review information that has been noted by the patient about doses taken, concomitant medications, and adverse events
- Collect medication containers
- Verify treatment compliance through tablet count and review of information in the patient’s notes
- Collect information on any adverse events that have occurred since the previous contact

- Collect information on concomitant medications
- Administer questionnaire on the acceptability of deferiprone DR vs. that of Ferriprox

If deemed necessary, patients with ongoing laboratory-related events may be asked after the last dose to provide further blood samples until resolution.

## **5.2 Method of Assignment to Treatment**

All patients must have been on a stable regimen of Ferriprox IR tablets for at least the past 3 months, and will be assigned to take deferiprone DR at approximately the same daily dosage that they are currently on. Those who are presently on Ferriprox at a dosage closer to 75 mg/kg/day will be assigned to Group A, and those who are presently on Ferriprox at a dosage closer to 100 mg/kg/day will be assigned to Group B. In both cases, the total dosage of deferiprone DR will be as close as possible to that of Ferriprox, but divided b.i.d. instead of t.i.d.

## **5.3 Blinding Procedures**

Not applicable. This study is open label.

## **5.4 Allocation of Patient Numbers**

After provision of informed consent, each patient will be assigned a unique ID number, and will be identified in all study data by this number rather than by name. The ID number will consist of 6 digits, where the first 3 digits represent the site code (001 for site #1, 002 for site #2, etc.) and the next 3 digits are assigned sequentially for each individual enrolled at that site. For example, if site #1 enrolls 8 patients, the ID numbers will be 001001 to 001008. The assigned ID numbers of patients who are screening failures or who withdraw from the study will not be reused.

## **5.5 Treatment Compliance**

Compliance will be determined as follows: 1) the patient will keep a daily record of the number of tablets taken, and 2) at Day 28, the investigator or a delegate will inspect the medication containers, whether empty, partly used, or unopened, and will check the number of tablets remaining. Compliance will be calculated by the number of tablets taken divided by the number of tablets prescribed. Any discrepancies must be discussed with the patient and documented in the source documents. Reasons for non-compliance with the treatment will be recorded in the source document and in the eCRFs. The investigator should discuss treatment compliance with the patient at each visit or during each telephone call.

If the number of returned tablets is less than it should be but the patient reports having taken the correct amount of medication, the site will report compliance as 100% in the eCRF, and will provide the reason for the apparent over-compliance (e.g., tablets were accidentally spoiled and could not be ingested), along with the actual percentage. Both under-compliance < 80% and over-compliance >120% will be reported as a protocol deviation, unless under-compliance is due to treatment interruption because of infection or neutropenia or other extenuating circumstances (see [Section 7.1.1.8](#)).

## **6 STUDY TREATMENTS**

All patients will be treated with deferiprone delayed release 1000 mg tablets at approximately the same total daily dosage that they had been prescribed for Ferriprox .

### **6.1 Investigational Product**

Deferiprone delayed release (DR) 1000 mg is a white to off-white, capsule-shaped, beveled edge, biconvex coated tablet, engraved with “FPX” score “DR” on one side and “APO” score “1000” on the other side. The tablets are manufactured by Apotex Inc., and will be supplied to the clinical site by ApoPharma Inc.

#### **6.1.1 Dosage Form and Mode of Administration**

Deferiprone DR tablets are to be taken twice a day, approximately 12 hours apart. The route of administration is oral. All patients will take approximately the same total daily dosage that they were taking three times a day with Ferriprox IR, whether that dosage was closer to 75 mg/kg/day (Group A) or closer to 100 mg/kg/day (Group B). The dosage for each subject will be rounded to the nearest multiple of 500 mg. The tablets are scored in a way that they can be split into two halves that maintain the release characteristics of the whole tablets.

#### **6.1.2 Precautions for Use**

The tablets are to be kept in a tightly closed bottle in order to protect them from moisture. The bottles are to be kept out of the sight and reach of children.

### **6.2 Packaging and Labeling**

The tablets are packaged in 75 cc opaque, white, round high-density polyethylene (HDPE) bottles with induction seals and child-resistant caps. The bottles contain 50 tablets and a desiccant bag, and will bear a label whose content is in accordance with all applicable regulatory requirements.

### **6.3 Shipping and Storage**

The study medication at each site will be kept in a secure location (a locked room or cabinet) under adequate storage conditions, as per label requirements, under the control of the investigator and with access to authorized individuals only. Product is to be kept at room temperature (15–30 °C / 59–86 °F). The room must have a calibrated digital temperature-monitoring device, and site personnel must use a temperature log to facilitate daily recording of the temperature of the storage facility. Temperature deviations must be immediately reported to the sponsor for investigation and determination of impact on the study medication.

Each shipment of investigational product will include shipment documents, which the investigator or a designate must complete as per the provided instructions and retain the original copies in the Investigator Trial File.

### **6.4 Product Accountability**

It is the responsibility of the investigator to ensure that all study drug received at the study center is inventoried and accounted for throughout the study. Records of receipt, storage and administration of the study drug supplied must be maintained, and drug accountability will be performed. At the conclusion of the study, a final inventory must be performed by the investigator or delegate. The sponsor will be responsible for determining the specific conditions for destruction of unused product.

### **6.5 Replacement Doses**

Patients who report that their medication has been lost or damaged will need to return to the study site to receive replacement tablets. Requests for replacement must be made in writing to the sponsor by the qualified staff member. All information related to the lost or damaged medication and the replacement medication is to be recorded in the drug accountability forms and patient source data.

### **6.6 Disposition of Unused Product**

All investigational product (IP) that is unused for any other reasons will be returned to the sponsor or discarded by the site according to internal procedures, if approved, in writing, by the sponsor. Destruction certificates for the completed destructions (or proof that IP was sent for destruction) will be obtained. The destruction may take place only after written approval by the sponsor.

## 7 MEASUREMENTS AND EVALUATIONS

### 7.1 Safety Measurements

#### 7.1.1 Medical Events, Adverse Events, and Serious Adverse Events

##### 7.1.1.1 Definition of Medical Events and Adverse Events

*Medical Event (ME):* Any new untoward medical occurrence or worsening of a pre-existing condition in a clinical trial participant that occurs after signing the informed consent form (ICF) but before receiving the first dose of study drug.

*Adverse Event (AE):* Any untoward medical occurrence in a patient who is administered a pharmaceutical or other therapeutic product in a clinical study, not necessarily having a causal relationship with the product. An AE can therefore be any unfavorable and unintended sign, symptom, or disease temporally associated with the use of a product, whether or not considered related to that product.

AEs include:

- Exacerbation of a pre-existing illness, including acute episodes/crisis of a chronic underlying condition
- An increase in frequency or intensity of a pre-existing episodic event or condition
- A condition detected or diagnosed after study treatment administration, even though it may have been present prior to the start of the study
- A continuous persistent disease or symptom present at baseline that worsens following the start of the study
- Accidents (e.g., involving a motor vehicle)
- Reasons for changes in concomitant medication (type of drug and/or dose)
- Medical, nursing, or pharmacy consultation
- Admission to hospital and surgical operations
- Abnormalities in laboratory findings (e.g., clinical chemistry, hematology, urinalysis), ECG, or other assessments (e.g., vital signs) that are not part of a larger medical condition already recorded as an AE and which are judged by the investigator to be clinically significant. The investigator should exercise medical and scientific judgment in deciding whether an abnormal laboratory finding or other abnormal assessment is clinically significant.

AEs do not include:

- A pre-existing disease or condition present or detected at the start of the study that does not worsen
- Hospital admissions or surgical procedures that had been planned prior to enrolment into the study
- The disease or disorder being studied, or a sign or symptom associated with that disease or disorder, unless it has worsened
- An overdose of either the study treatment or concurrent medication without any signs or symptoms

#### **7.1.1.2 Monitoring and Documenting of Medical Events and Adverse Events**

Prior to enrolling a patient, study site personnel will note the occurrence and nature of any medical condition(s) in the source documents and the appropriate section of the eCRF. During the study, they will note any change in the condition(s), and the occurrence and nature of any MEs/AEs. MEs will be collected from the time the ICF is signed until the first dose of study drug, and AEs will be collected from the time the treatment starts until 30 days after the last dose.

AEs and SAEs that are related to the underlying medical condition for which the patient enrolled in the clinical trial will be recorded separately from others.

Patients will be instructed to report any MEs/AEs to the investigator or a delegate. In addition, at site visits and telephone calls, the investigator will solicit information about the occurrence of MEs/AEs through open-ended, non-leading verbal questions such as:

- How are you feeling?
- Have you had any medical problems since the last visit?
- Have you taken any new medications, other than that provided in this study, since the last visit?

Based on the patient's response to these questions, the investigator or delegate should ask additional questions relevant to the specific complaint, such as:

- How severe is/was the symptom?
- How often did the symptom occur?
- How long did the symptom last?

The patient should also be questioned about any previously reported AEs that have not resolved.

The investigator will evaluate all AEs/MEs for their relationship to the investigational product (Section 7.1.1.3), intensity (Section 7.1.1.4), and seriousness (Section 7.1.1.5), and will document any measures taken to address the event. There should be an attempt to establish a diagnosis of the AE based on signs, symptoms, and/or other clinical information. Wherever possible, a diagnosis should be documented, rather than the individual signs/symptoms. All information is to be clearly recorded in the source documents.

If the dosage of study drug is reduced or treatment is discontinued as a result of an AE, the circumstances leading to such reduction or discontinuation must be clearly documented.

All AEs must be followed until resolution, the condition stabilizes, the event is otherwise explained, or the patient is lost to follow-up. The investigator is responsible for ensuring that follow-up includes any supplemental investigations that are needed to elucidate the nature and/or causality of the AE as completely as possible. This may include additional laboratory tests or investigations, histopathological examinations, or consultation with other health care professionals.

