Study design (cont'd):	
Screening will be conducted within 14 days prior to the start of dosing, and with the exception of hematology, laboratory results obtained at that time will be treated as the baseline values. Blood samples will be collected for the assessment of biochemistry (screening and Days 3, 7, 14, 21, and 28), hematology (screening, baseline, and Days 7, 14, 21, and 28), serology (screening only), and other safety parameters (screening and Day 28); and urine samples will be collected for urinalysis (screening and Day 28). For the Day 3, 7, 14, and 21 samples, patients may choose to visit a local laboratory instead of the study site; if this is done, they must use the same laboratory throughout the entire study. If deemed necessary, patients with ongoing adverse events may be asked after the last dose to provide further blood samples until resolution. On Day 28, patients will be asked for their views on the acceptability of the delayed release formulation vs. the immediate release (Ferriprox) tablets.
 
Any patient who withdraws before completing treatment will be requested to return for an Early Termination visit, at which time the procedures scheduled for the Day 28 visit will be conducted.
 
As this will be the first time that deferiprone DR is administered to patients with iron overload, as a precaution, enrollment will be conducted progressively in small groups, and safety results will be reviewed following the enrollment of a limited number of patients. Decisions regarding continuation will be based on the findings.
	
Duration of participation:	
The duration of participation will be 28 days, excluding the screening period.
	

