Screening will be conducted within 14 days prior to the start of dosing, and with the exception of hematology, laboratory results obtained at that time will be treated as the baseline values. Blood samples will be collected for the assessment of biochemistry (screening and Days 3, 7, 14, 21, and 28), hematology (screening, baseline, and Days 7, 14, 21, and 28), serology (screening only), and other safety parameters (screening and Day 28); and urine samples will be collected for urinalysis (screening and Day 28). For the Day 3, 7, 14, and 21 samples, patients may choose to visit a local laboratory instead of the study site; if this is done, they must use the same laboratory throughout the entire study. If deemed necessary, patients with ongoing adverse events may be asked after the last dose to provide further blood samples for up to 30 days or until resolution. On Day 28, patients will be asked for their views on the acceptability of the delayed release formulation vs. the immediate release (Ferriprox) tablets. Any patient who withdraws before completing treatment will be requested to return for an Early Termination visit, at which time the procedures scheduled for the Day 28 visit will be conducted.

As this will be the first time that deferiprone DR is administered to patients with iron overload, as a precaution, enrollment will be conducted progressively in small groups, and safety results will be reviewed following the enrollment of a limited number of patients. Decisions regarding continuation will be based on the findings. Details are provided in [Section 3.1.1](#).

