#### **4.5 Patient Withdrawal**

Patients have the right to withdraw from the study at any time and for any reason without consequence to future care by the investigator or study center.

A patient may be withdrawn from the study at any time, at the discretion of the investigator, for any of the following reasons:

- Medical or safety reasons considered significant by the patient and/or the investigator
- Requirement for concomitant medication that might interfere with the evaluation of study treatment or may be contraindicated
- Receipt of a rescue medication
- Occurrence of other illnesses that might affect the patient's further participation in the study or evaluation of study treatment
- A protocol deviation that might interfere with study assessments, as judged by the investigator
- Repetitive patient non-compliance with the protocol or with instructions of the investigator
- Participation in another clinical trial at any time during the conduct of this study
- Any other situation where, in the opinion of the investigator, continuation of the study would not be in the best interest of the patient

A patient **must** be withdrawn from the study if any of the following conditions apply:

- Pregnant or planning to become pregnant (see [Section 7.1.4](#))
- A confirmed ALT or AST value  $>10 \times \text{ULN}$  (see [Sections 4.5.1.1](#) and [7.1.1.8.1](#))
- A confirmed ANC value  $< 0.5 \times 10^9$  (see [Sections 4.5.1.2](#) and [7.1.1.8.2](#))
- Occurrence of any adverse event characterized as life-threatening or disabling that is not associated with the patient's condition
- Termination of the study by the sponsor

Patients who decide to withdraw participation in the study should always be contacted, if possible, in order to ask about the reason for withdrawal, whether any adverse events (AEs) occurred, and use of concomitant medications. A withdrawn patient should return for an early termination visit and a follow-up visit. All investigational product and materials should be returned. If any AEs occurred, the investigator must attempt to follow up the outcome until resolution.

If a patient withdraws or is withdrawn before completing the study, the date and reason for the withdrawal must be entered on the source document and on the appropriate page of the electronic case report form (eCRF), and all other appropriate eCRF pages must be completed.

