#### **4.6 Prior and Concomitant Therapies**

To be considered for enrollment, patients cannot be taking any iron chelator other than Ferriprox. Those who are on a combination regimen of Ferriprox and another product are not eligible.

In addition, during the trial, they may not take any other investigational product, or any drugs that are known to cause agranulocytosis. Medications that are being taken on a stable regimen and that are considered necessary for the subject's welfare may continue to be taken, at the discretion of the investigator. All medications (including study product, herbal medications, and over-the-counter medications) and nutritional supplements taken from 3 months prior to screening up to the end of the study (Day 28 or early termination) must be reviewed by the investigator and recorded in the source document and in the appropriate section of the eCRF.

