**Table 5.1 Table of study procedures**

Study Procedure	Screening Day -14 to -1	Baseline Day 0	Day 3 (±1 day)	Day 7 (±1 day)	Day 14 (±2 days)	Day 21 (±2 days)	Day 28 (±2 days) or early termination 
Informed consent	X						
Demography	X						
Medical history 	X						
Medication history	X	X					
Eligibility criteria	X	V					
Biochemistry 	X		X	X	X	X	X
Hematology 	X	X		X	X	X	X
Coagulation 	X						X
Serology 	X						
Urinalysis 	X						X
Physical examination 	X						X
Vital signs	X						X
Serum pregnancy test 	X						X
Dispense study medication		X					
Dosing	Twice-daily from Day 1 to Day 28						
Collect study medication containers							X
Treatment compliance							X
Medical events	X	X					
Adverse events/ serious adverse events	Throughout the study						
Concomitant medications	Throughout the study						
Acceptability questionnaire							X

V: Verify

1. If deemed necessary, patients with ongoing adverse events may be asked after the last dose to provide further blood samples until resolution
2. Medical history is to include a record of at least 10 measured ALT and AST levels
3. Biochemistry: Total protein, gamma-glutamyl transferase (GGT), lactate dehydrogenase (LDH), sodium, potassium, chloride, glucose, bilirubin (total, direct, and indirect), alanine aminotransferase (ALT), aspartate aminotransferase (AST), albumin, blood urea nitrogen, calcium, creatinine, uric acid, alkaline phosphatase, amylase, serum ferritin, and blood iron
4. Hematology: Hemoglobin, total WBC count, ANC, MCV, and platelet count
5. Coagulation: Prothrombin Time (PT), Partial Thromboplastin Time (PTT), and International Normalized Ratio (INR)
6. Serology: HIV Ag/Ab Combo, hepatitis B (HBsAg (B)), and hepatitis C (anti-HCV (C))
7. Urinalysis: Color, appearance, specific gravity, pH, leukocyte, protein, glucose, ketones, bilirubin, blood, nitrite, urobilinogen. Microscopic examination must be performed if dipstick test is outside the reference range for leukocyte, blood, nitrite or protein. (Note: for patients with sickle cell disease, samples are to be sent for microscopy if there is blood in the urine or three or more “plus signs” for protein.)

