#### **7.1.1.6 Reporting of Serious Adverse Events**

All SAEs occurring up to 30 days following completion of or discontinuation from the study must be reported to the sponsor, regardless of whether they are suspected of having a causal relationship with the study drug. Any SAEs for which the investigator does suspect a causal relationship must be reported to the sponsor regardless of the time elapsed since the last dose of the study drug.

Patients will be instructed to report SAEs to the investigator **within 24 hours**, by telephone. In turn, the investigator must report all SAEs to the sponsor **within 24 hours** of occurrence or notification by the patient, using the sponsor's SAE form. The sponsor will provide contact information for reporting SAEs. An assessment of causality must be provided at the time of the initial report. In the case of an SAE that is fatal or life-threatening, the investigator or delegate must then complete and submit a follow-up SAE form to the sponsor **within 5 calendar days**, and must submit further follow-up forms if additional relevant follow-up information becomes available.

The sponsor will submit reports of SAEs to the appropriate regulatory agencies, in line with local regulatory requirements and timelines.

Investigators must report all SAEs to their IRB/IEC as well as to the sponsor. If any SAE that is considered at least possibly related to the study medication and is unexpected occurs at one site, the sponsor will promptly inform all other sites of this, and all investigators must then report this event to their own IRBs/IECs, following the same timelines as above or following local IRB/IEC policy, whichever takes precedence.

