#### **7.1.1.7 Follow-up and Documentation of SAEs**

SAEs that occur during the study and up to 30 days after the last dose of study drug must be documented in the patient's medical record and on the SAE report form. The investigator should attempt to establish a diagnosis of the event based on signs, symptoms, and/or other clinical information. In such cases, the diagnosis rather than the individual signs/symptoms should be documented as the SAE.

All SAEs must be followed until resolution, the condition stabilizes, the event is otherwise explained, or the patient is lost to follow-up. The investigator is responsible for ensuring that follow-up includes any supplemental investigations that may be indicated, in order to elucidate the nature and/or causality of the SAE as completely as possible. This may include additional laboratory tests or investigations, histopathological examinations, or consultation

with other health care professionals. The sponsor may request that the investigator perform or arrange for the conduct of supplemental measurements and/or evaluations.

If a patient dies during participation in the study or during a specified follow-up period, the sponsor should be sent a copy of any post-mortem findings, including histopathology.

New or updated information is to be recorded on the originally completed SAE report form, with all changes signed and dated by the investigator.

The clinical research associate (CRA) will verify the original SAE report form against the source documents at the next monitoring visit.

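### No scheduled contact supports the 30-day post-dose window for adverse events, so new events after Day 28 depend on patients reporting them unprompted

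*Combined protocol and SAP*

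**What the plan says.** Three sections set the safety window:

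- Section 7.1.1.2, for AEs: "AEs will be collected from the time the treatment starts until 30 days after the last dose".
- Section 7.1.1.6, for SAE reporting: "All SAEs occurring up to 30 days following completion of or discontinuation from the study must be reported to the sponsor".
- Section 7.1.1.7, for SAE documentation: "SAEs that occur during the study and up to 30 days after the last dose of study drug must be documented".

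The schedule stops earlier:

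- The Synopsis states: "The duration of participation will be 28 days, excluding the screening period".
- Table 5.1 gives dosing as "Twice-daily from Day 1 to Day 28". Its last column is Day 28 (±2 days) or early termination, and its AE row has no column beyond that. Section 5.1 ends at the same visit and allows telephone contact only in place of the visits between baseline and Day 28.
- Section 4.6 requires medications to be recorded "up to the end of the study (Day 28 or early termination) must be reviewed by the investigator".
- Section 4.5 adds, for withdrawals: "A withdrawn patient should return for an early termination visit and a follow-up visit". Neither Table 5.1 nor Section 5.1 describes that second visit.

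**The concern.** Section 7.1.1.2 has staff ask open questions about new events whenever they see or telephone the patient. With nothing scheduled after Day 28, a completer with no ongoing event is not asked again, and the record of post-dose events depends on what that patient volunteers. Few late events in the tables could then mean that few occurred or that nobody asked.

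This matters because the primary objective is safety, this is the first use of DR in iron-overloaded patients, and the Synopsis lists frequency, intensity, onset, duration and relatedness of AEs and SAEs among the evaluations. Attribution is also harder in this period. Section 3.1 returns patients to their regular chelation after the last dose, and Section 7.1.1.3 asks the investigator to weigh other drugs and the response to withdrawal, but medication is no longer being recorded. The plan itself treats the post-dose period as relevant: Section 7.1.1.8.2 asks for infection symptoms to be reported in the first week after treatment.

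**Working it through.** The plan gives no figure for the share of the window that is covered, so there is none to reproduce. The check sets the stated window against the scheduled contacts.

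**Inputs**
- Dosing runs from Day 1 to Day 28 (Table 5.1).
- The AE window ends 30 days after the last dose (Section 7.1.1.2).
- The last scheduled contact is Day 28 ± 2, that is, Day 26 to Day 30 (Table 5.1, Section 5.1).
- Assumption: the last dose is on Day 28 whatever the visit day.

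**Formulas**
- End of window = 28 + 30 = Day 58.
- Days after the last scheduled contact = 58 − visit day.
- Share = those days / 58.

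**Results for a completer**

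| Last contact | Days without scheduled contact | Share of 58 days | Post-dose days covered (of 30) |
|---|---|---|---|
| Day 26 | 58 − 26 = 32 | 55.2% | 0 |
| Day 28 | 58 − 28 = 30 | 51.7% | 0 |
| Day 30 | 58 − 30 = 28 | 48.3% | 2 (6.7%) |

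If the last dose instead fell on the visit day, the gap would always be 30 days: 30/56 = 53.6% for Day 26 and 30/60 = 50.0% for Day 30, inside the same range.

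**What reaches the patient after Day 28**
- Known AEs are followed until they resolve, settle, are explained, or contact is lost (Section 7.1.1.2). Patients meeting the liver-enzyme criteria are followed past Day 28 if needed (Section 7.1.2). Both provisions serve events already identified.
- Extra blood samples are discretionary and only for patients with ongoing events (Section 3.1, Table 5.1 note 1, Section 5.1).
- Patients are told to report AEs themselves (Section 7.1.1.2), to telephone SAEs within 24 hours (Section 7.1.1.6), and to report infection symptoms (Section 7.1.1.8.2).
- A withdrawn patient's early termination visit may fall up to one month after the last dose (Section 5.1, baseline instructions), so it may cover part or most of that patient's window. Completers have no counterpart.

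Only patient-initiated reporting can bring in a new event from a completer who had nothing ongoing at Day 28.

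**Endpoints**
- The ALT/AST primary endpoint (Section 9.1.1) rests on scheduled samples at Days 3, 7, 14, 21 and 28, before the gap.
- Acceptability is measured at Day 28.
- Section 9.1.2 counts GI distress over the study without saying whether the 30 post-dose days belong to it.
- The AE and SAE tables are the outputs that cover the whole window.

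**The case against.** The strongest reply is that a collection window served by patient reporting is a weak design but not a contradiction, and that little depends on it. After Day 28 patients resume their regular regimen, which by eligibility is Ferriprox, the same active ingredient, so late events would be hard to attribute to DR. The primary endpoint is untouched, and GI distress reads most naturally as confined to the 28 days. Much of this stands: it keeps the point to the AE and SAE summaries. It does not remove it, because the plan chose a 30-day window and following it exactly gives solicited ascertainment in one part and unsolicited in the other. Difficulty of attribution is a reason to record the medication taken and to separate the two periods.

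Four stronger readings are tempting, and the documents do not support them:

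- A reader might infer that the window is not observed at all. Self-reporting of AEs and SAEs is required, so the accurate statement is that new events are not actively sought.
- A reader might infer that completers are never contacted again. Those with ongoing events or liver-enzyme elevations meeting the criteria are followed.
- A reader might multiply 30 patients by 30 days and say that 900 patient-days are counted as observed. That product is only a ceiling on unsolicited time. Section 9.4.1.3 plans patient-level incidences and frequency tables, with no person-time denominator.
- A reader might take Section 3.1, which lets patients be asked to "provide further blood samples for up to 30 days or until resolution", as a cap on follow-up. The sampling is discretionary, the phrase offers resolution as an alternative, and the mandatory rule in Section 7.1.1.2 sets no such limit.

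It might also be argued that completers and withdrawn patients are ascertained differently. That is possible, but no planned analysis compares them.

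**Conclusion.** The point holds as a mismatch between the stated safety window and the schedule meant to serve it. For a completer, about half of the 58-day AE window (48% to 55%, depending on the visit day and assuming the last dose on Day 28) falls after the last scheduled contact. New events there are captured passively, without concurrent medication records. The Section 4.5 follow-up visit cannot be carried out as written because its timing and content are undefined.

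The consequence is limited to possible under-recording and unclear attribution of late AEs and SAEs. The documents do not allow the number of missed events to be estimated, and nothing shows that a conclusion about DR would change. This is a worthwhile, inexpensive improvement and not a flaw in the primary analysis.

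**What to change.** - Add one telephone safety contact at about 30 days after the last dose to Table 5.1 and Section 5.1, for completers and withdrawn patients, covering AEs, SAEs and concomitant medications, including the chelator resumed.
- State that this call is the follow-up visit named in Section 4.5.
- Align the Synopsis participation period (28 + 30 = about 58 days, plus screening) and the Section 4.6 recording period with the AE window.
- In Section 9.4.1.3, tabulate events on DR separately from events after the last DR dose, and in Section 9.1.2 say which period counts for GI distress.

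The cost is about 30 short calls by existing site staff and a protocol and consent wording change. A call will not detect asymptomatic laboratory changes. The alternative is to shorten the collection window to the scheduled contacts and label later reports as spontaneous. That also makes the sections agree, but gives up systematic post-dose information.
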